## **9.5 Safety Subgroup Analyses**

No safety subgroup analyses are planned.

## **9.6 Other Safety Analyses**

COVID-19 impact on participants' disposition, protocol deviation, site visits and missed assessments and COVID-19 vaccine will be summarized. A summary of AEs related to COVID-19 will also be provided.

### **9.6.1 Electrocardiogram**

Descriptive statistics for 12-lead ECG parameters (heart rate, PR interval, QRS interval, QT interval, and QTc interval) at baseline, postbaseline, and changes from baseline values at each postbaseline timepoint will be presented by study intervention. An assessment will be assigned to the most recently administered study intervention.

ECG parameter values are considered PCS if ECG values meet either the actual value or change from baseline PCS high criteria listed in Table C-4. The number and percentage of participants with PCS postbaseline values will be tabulated by study intervention. The percentages will be calculated relative to the number of participants with an available non-PCS baseline value and at least 1 postbaseline assessment. The numerator will be the total number of participants with an available non-PCS baseline value and at least 1 PCS postbaseline ECG value.

A supportive listing of participants with PCS postbaseline values will be provided. A listing of all AEs for participants with PCS ECG values will also be provided.

### **9.6.2 Suicidality Assessment**

For the C-SSRS, the number and percentage of participants with suicidal ideation and suicidal behavior in lifetime history, 6 months prior to screening, and post the study intervention will be summarized by study intervention for the safety population. An

assessment will be assigned to the most recently administered study intervention. The assessment collected at each visit will be summarized.

A supportive listing of participants with suicidal ideation or suicidal behavior will be provided for the safety population.

## **10.0 Other Analyses**

### **10.1 Additional Health Economics Outcomes Research (HEOR) Analyses**

Satisfaction with study medication responder is defined as response to the Satisfaction with Study Medication question of 'Satisfied' or 'Extremely Satisfied.' The same GLMM model for the primary endpoint will be performed at 8 hours and 24 hours, separately. Descriptive statistics at 8 hours and 24 hours after taking double-blind study intervention will be presented by study intervention.

The ordinal activity limitation will be analyzed using Cochran-Armitage trend test. In addition, responder analyses will be performed using the same GLMM model. A participant will be defined as a responder if the participant records not at all limited - I could do everything or a little limited, and a non-responder otherwise. Descriptive statistics at 24 hours taking double-blind study intervention will be presented by study intervention.

For FDS, by timepoint analysis will be performed using the same primary GLMM model with an additional covariate of predose baseline FDS score at 1, 2, 3, 4, 6, 8, and 24 hours. Additional endpoint will be defined as a responder if a participant records no disability, able to function normally at all the observed timepoints FDS (1, 2, 3, 4, 6, 8, and 24 hours postdose), and a non-responder otherwise. The data will be analyzed using the same primary GLMM model with an additional covariate of predose baseline FDS score.

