8.10. Health Economics Outcomes Assessments

Functional Disability Scale

The FDS is a single item used to measure the participant's level of functional disability (Cady 2015, Tepper 2015). Participants will be asked to rate the performance of daily activities using 4 response options ranging from 0 (no disability, able to function normally) to 3 (severely impaired, cannot do all or most things, bed rest may be necessary). The measure will be assessed at predose (baseline) and 1, 2, 3, 4, 6, 8, 24, and 48 hours after double-blind study intervention for treating the first and second qualifying prodrome events.

Satisfaction with Study Medication

Overall satisfaction with study medication for migraine will be assessed using a single item and 7-point rating scale ranging from extremely satisfied (0) to extremely dissatisfied (6). The question will be answered by the participants in their eDiary at 8 hours and 24 hours after taking double-blind study intervention for treating the first and second qualifying prodrome events.

Activity Limitation

A single-item measure assessing activity limitation based on a 24-hour recall will be administered as an additional health outcome measure. The measure will be used to evaluate activity limitation with a 5-level response ranging from "Not at all limited – I could do everything" to "Extremely limited." The measure will be administered at 24 hours after taking double-blind study intervention.

9. Statistical Considerations

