### **3.5 Additional HEOR Endpoint(s)**

To evaluate the effect of a single dose of ubrogепant (100 mg) versus placebo, administered during the prodrome, on satisfaction and Activity Limitation:

- Satisfaction with study medication at 8 and 24 hours after taking double-blind study intervention during the prodrome
- Activity Limitation within 24 hours after taking double-blind study intervention during the prodrome.

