A single-item measure assessing activity limitation based on a 24-hour recall will be administered as an additional health outcome measure. The measure will be used to evaluate activity limitation with a 5-level response ranging from "Not at all limited – I could do everything" to "Extremely limited." The measure will be administered at 24 hours after taking double-blind study intervention.

The following are general considerations for efficacy analyses:

- Efficacy analyses will be performed based on mITT population.
- Continuous variables will be summarized by number of participants with observed values (n), mean, standard deviation (SD), median, 1st and 3rd quartiles (Q1, Q3), minimum (min), and maximum (max).
- Categorical variables will be summarized by number of participants with observed values or events and percentages based on the specified population.
- The efficacy analyses will be performed using a GLMM in the observed binary response variable unless an imputation method is specified.
- The least squares mean (LSMEAN) estimates of the treatment effects for the primary and secondary endpoints alongside its 95% CI will be presented.

- All statistical hypothesis tests will be performed at the 2-sided 5% significance level.
- Efficacy analyses will be presented by treatment or study intervention randomized (placebo or ubrogepant 100 mg).

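### The 7-point satisfaction item is tested only as a satisfied/not-satisfied responder at 8 and 24 hours; an ordinal comparison on the full 0-6 score should be added beside it

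*SAP*

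**What the plan says.** Protocol 8.10 describes satisfaction as a single eDiary item ("7-point rating scale ranging from extremely satisfied (0) to extremely dissatisfied (6"), answered 8 and 24 hours after each dose. SAP 3.5 lists the endpoint as "Satisfaction with study medication at 8 and 24 hours after taking double-blind study intervention during the prodrome", with no cut. Protocol 9.4.1.4 leaves the method to the SAP.

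SAP 10.1 then supplies it: "Satisfaction with study medication responder is defined as response to the Satisfaction with Study Medication question of 'Satisfied' or 'Extremely Satisfied". For the model it says "The same GLMM model for the primary endpoint will be performed at 8 hours and 24 hours, separately". The GLMM in SAP 8.3.3 assumes a binary response with a logit link. The only other output for satisfaction is: "Descriptive statistics at 8 hours and 24 hours after taking double-blind study intervention will be presented by study intervention".

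The next paragraph of SAP 10.1 treats the five-level activity-limitation item differently. "The ordinal activity limitation will be analyzed using Cochran-Armitage trend test", and then "In addition, responder analyses will be performed using the same GLMM model".

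SAP 8.1 sets the level: "All statistical hypothesis tests will be performed at the 2-sided 5% significance level". SAP 12.0 confines type I error control to the primary and three secondary endpoints. Satisfaction is an additional HEOR endpoint, and neither document plans power for it.

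**The concern.** The endpoint is satisfaction on a graded scale, but the only treatment comparison asks whether a participant reached 'Satisfied' or better. A move from dissatisfied to the middle of the scale, or from 'Satisfied' to 'Extremely Satisfied', does not affect the test. Neither document gives a reason for the cut, or for giving the longer scale less than the shorter one beside it.

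At stake is the information yielded by data the eDiary already collects. A real but broad shift in satisfaction could be missed, or reported with a wider interval than necessary. Any full-scale test run after unblinding would be a post hoc choice.

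**Working it through.** **The plan's own figure.** There is none for satisfaction. The only power statement (Protocol 9.2, SAP 2.4) concerns the primary endpoint: 64% against 80%, 240 per treatment, at least 95% power. It reproduces. z = 0.16 / √[(0.64×0.36 + 0.80×0.20)/240] = 0.16/0.0403 = 3.97, and Φ(3.97 − 1.96) = 98% (97.6% with a pooled null variance). It says nothing about satisfaction.

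**Assumptions.** From the documents: seven categories, two-sided 5%, and 240 per treatment borrowed from the primary calculation. Not in the documents, so assumed: the placebo distribution, the odds ratio, the number of participants with both events, and the within-participant correlation. I also take 'Satisfied' to be the second category. The documents label only the ends of the scale, so this is likely but not stated.

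**Step 1: information under proportional odds.** With N observations in two equal groups, category proportions pᵢ and responder proportion p, the information on the log odds ratio is

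- full scale: (N/12)(1 − Σpᵢ³)
- responder: (N/4) p(1 − p)
- ratio: (1 − Σpᵢ³) / [3p(1 − p)]

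For a uniform placebo distribution (each pᵢ = 1/7, p = 2/7), the ratio is (48/49)/(30/49) = 1.60.

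**Step 2: power with 240 per treatment, independent groups, odds ratio 1.5.** For the uniform case the responder rate rises from 28.6% (odds 0.4) to 37.5% (odds 0.6). z = 0.0893/√[(0.2041 + 0.2344)/240] = 2.09, giving 55%. On the full scale the information is 40 × 0.9796 = 39.2, z = ln(1.5) × √39.2 = 2.54, giving 72%. The same steps for four assumed placebo distributions:

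| Placebo percentages, score 0 to 6 | Top two | Σpᵢ³ | Information ratio | Responder power | Full-scale power |
|---|---|---|---|---|---|
| 3, 7, 12, 28, 20, 18, 12 | 10% | 0.0396 | 3.56 | 30% | 71% |
| 5, 10, 20, 30, 20, 10, 5 | 15% | 0.0453 | 2.50 | 39% | 71% |
| uniform | 29% | 0.0204 | 1.60 | 55% | 72% |
| 15, 25, 20, 20, 10, 6, 4 | 40% | 0.0363 | 1.34 | 60% | 71% |

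Over odds ratios from 1.3 to 2.25 the loss runs from under 1 point (large effect, 40-50% satisfied on placebo) to 44 points (few satisfied on placebo). On precision, √1.34 = 1.16 and √3.56 = 1.89, so the interval for the log odds ratio would be 16% to 89% wider in these cases.

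**Step 3: paired illustration.** This assumes 430 complete pairs (430/516 = 83% of those randomized), 30% in the top two on placebo and an odds ratio of 1.3. Trials were simulated from correlated latent normal scores. A paired z-test on the responder indicator was compared with one on ridit scores.

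| Latent correlation | Responder | Full scale |
|---|---|---|
| 0 | about 45% | about 59% |
| 0.3 | about 52% | about 72% |
| 0.6 | about 65% | about 91% |

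With no effect, both tests rejected in about 5% of trials. Other seven-category shapes with the same 30% moved these figures by no more than about 3 points. The z-tests stand in for the GLMM and the cumulative-logit model and carry no period term.

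**Step 4: effects that are not proportional odds.** With 240 per treatment:

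- Take the 15% distribution and move 10% of participants just across the cut, from the third category to the second. Responder power is about 78%; full-scale power is about 8%.
- Take the 40% distribution, raise the top two to 50%, and scale the categories proportionally on each side of the cut. Responder power is 60%; full-scale power is 49%.

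The sign of the difference therefore depends on the shape of the effect.

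**The case against.** The strongest reply is that nothing planned fails. Satisfaction is exploratory, has no allocated alpha or power target, and has a prespecified cut, model and timepoints. That stands, and it limits the weight of this point.

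Second, dichotomizing graded ratings is the SAP's usual practice: headache intensity, the FDS secondary endpoint and prodrome symptoms are all handled that way, so activity limitation is the exception. This also stands. A reader might infer that the two HEOR paragraphs contradict each other. They do not, since nothing requires two items to share a method. The contrast shows only that the authors thought an ordinal test worthwhile for a similar item.

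Third, the Cochran-Armitage test is a poor template. As named, it ignores pairing and period. In simulated paired data its null rejection rate was about 1-3% instead of 5%, and at a correlation of 0.4 it gave back much of the ordinal gain. This is right, and it is why the fix does not copy that test.

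Fourth, a reader might infer that movement elsewhere on the scale goes unreported. The documents do not support that: descriptive statistics for satisfaction are promised by treatment, and the text does not limit them to the responder variable. What is missing is a test and an estimate.

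**Conclusion.** The point holds as a modest improvement. No inferential analysis of satisfaction uses the 0-6 scale. Under an approximately proportional-odds shift the dichotomy loses power in every case examined: about 45-65% against 59-91% in the paired illustration.

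A reader might infer a fixed loss that could be quoted for this trial. The documents support none, because they give no satisfaction distribution, effect size, correlation or number of complete pairs, and the result moves widely with each. Nor do they support the inference that the ordinal test is always better: it loses when the effect is concentrated at the cut. The comparison of precision likewise assumes a common odds ratio; without one, the responder and cumulative odds ratios measure different things. For these reasons the responder GLMM should keep its place and the ordinal model should be added to it. The primary and secondary conclusions are unaffected.

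**What to change.** In SAP 10.1, keep the responder GLMM at 8 and 24 hours as written. At each timepoint add a cumulative-logit (proportional-odds) model on the 0-6 score, with period and treatment as categorical fixed effects and within-participant clustering handled by GEE with empirical variance. Report the common odds ratio with its 95% CI beside the responder odds ratio. In the same sentence, state which scores count as 'Satisfied' and 'Extremely Satisfied'.

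The cost is one paragraph of SAP text and one extra model per timepoint. It needs no new data and does not change the sample size, the gatekeeping or any gated endpoint. The downside is reliance on an approximately common odds ratio across the cuts; the retained responder result helps to check that. The addition is worth most if written before unblinding.

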9.2. Sample Size Determination

The primary efficacy parameter is the absence of a headache of moderate/severe intensity within 24 hours after taking double-blind study intervention during the prodrome. Based on the assumption of a response rate of 64% for the placebo group and 80% for the ubrogepant 100 mg group, 240 participants in each study intervention will provide at least 95% power to detect the

above intervention difference at the 2-sided 5% significance level. The nQuery Advisor 7.0 was used for the power calculation.

A blinded sample size re-estimation has been performed as planned. Given that 7% of participants had no determinable primary endpoint as observed based on the data cut of July 5, 2021, approximately 516 participants will be randomized to maintain the effect sample size of 480 participants.

The actual power will be higher with the crossover design as some participants will contribute 2 qualifying prodrome events during the double-blind treatment period.

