9.4.1.2. Primary Analyses

The primary efficacy endpoint for the absence of a headache of moderate/severe intensity within 24 hours after taking double-blind study intervention during the prodrome will be analyzed using a GLMM based on determinable data on the primary efficacy endpoint. Specifically, the status of absence of a headache of moderate/severe intensity within 24 hours should be decided based on all observed data including headache reported at a series of scheduled timepoints, reported event-driven, 24-hour recall headache, and whether a participant took rescue medication. If a participant did not report moderate/severe headache and has a missing 24-hour recall assessment, that participant will be counted as indeterminable. This GLMM model assumes a binary distribution for the response and uses a logit link. The analysis model will include period, and treatment as categorical fixed effects. An unstructured covariance matrix will be used for the covariance matrix of the residual effect for the repeated measurements (corresponding to the 2 qualifying prodrome events) within a participant. The treatment difference in terms of odds ratio between ubrogepant 100 mg and placebo will be estimated from the GLMM model.

The carryover effect will be tested although no or very minimum carryover effect is expected as the minimum 7-day washout period is much longer than the 5 times of half-life. A similar GLMM model will be fitted. The model includes period and treatment as categorical fixed effects, and period-by-treatment interaction. The carryover effect will be tested using the confounded period-by-treatment interaction. If the carryover effect is significant, the analysis should use first period only data. For sensitivity analysis purpose, first period only data analysis will be performed regardless of the significance level of the carryover effect.

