## **8.4 Secondary Efficacy Analyses**

### **8.4.1 Secondary Efficacy Analyses**

The secondary hypotheses are stated as follows:

Secondary null hypothesis 1: Ubrogepant 100 mg is the same as placebo in the acute treatment of migraine when administered during the prodrome, as measured by the proportion of participants who do not develop headache of moderate/severe intensity within 48 hours after taking the double-blind study intervention during the prodrome.

Secondary alternative hypothesis 1: Ubrogepant 100 mg is different from placebo in the acute treatment of migraine when administered during the prodrome, as measured by the proportion of participants who do not develop headache of moderate/severe intensity within 48 hours after taking the double-blind study intervention during the prodrome.

Secondary null hypothesis 2: Ubrogepant 100 mg is the same as placebo in the acute treatment of migraine when administered during the prodrome, as measured by the proportion of participants who are able to function normally over 24 hours after taking the double-blind study intervention during the prodrome.

[figure not shown]
Secondary alternative hypothesis 2: Ubrogepant 100 mg is different from placebo in the acute treatment of migraine when administered during the prodrome, as measured by the proportion of participants who are able to function normally over 24 hours after taking the double-blind study intervention during the prodrome.

Secondary null hypothesis 3: Ubrogepant 100 mg is the same as placebo in the acute treatment of migraine when administered during the prodrome, as measured by the proportion of participants who do not develop headache of any intensity within 24 hours after taking the double-blind study intervention during the prodrome.

[figure not shown]
Secondary alternative hypothesis 3: Ubrogepant 100 mg is different from placebo in the acute treatment of migraine when administered during the prodrome, as measured by the proportion of participants who do not develop headache of any intensity within 24 hours after taking the double-blind study intervention during the prodrome.

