**Figure 3. Determination of absence of moderate/severe headache within 48 hours (responder)**

**Figure 4. Determination of absence of any intensity headache within 24 hours (responder)**

The first and third secondary endpoints (i.e., the absence of a headache of moderate/severe intensity within 48 hours and absence of a headache of any intensity within 24 hours after taking double-blind study intervention during the prodrome) will be analyzed using a GLMM model based on observed data similar to the one used for the analysis of the primary endpoint.

A sensitivity analysis will impute participants with indeterminable status as non-responders. An additional sensitivity analysis will use the multiple imputation approach described for the primary endpoint to impute the missing headache occurrence status within 24 hours/48 hours for the participant for each qualifying prodrome event with an unknown status of headache occurrence within 24 hours/48 hours after taking double-blind study intervention.

Another sensitivity analysis will assume missing prodrome events as MNAR. Analyses using only first period data will also be performed as a sensitivity analysis using logistic regression model.

The second secondary endpoint, i.e., ability to function normally over 24 hours after taking double-blind study intervention during the prodrome, includes the repeated measures of dichotomized FDS response at each postdose timepoint over 24 hours. The dichotomized response takes value 1 if the participant records no disability, able to function normally on the FDS, and takes value 0 otherwise. The repeated binary responses will be analyzed using a GEE model with a logit link. The GEE model will include period, treatment, time, treatment-by-time interaction as categorical fixed effects, predose baseline FDS score for the period, and predose baseline-by-time interaction as covariates. An unstructured working correlation matrix will be used for the repeated measures within each participant. If the unstructured correlation matrix does not converge, an unstructured correlation matrix or a working m-dependent ( $m=6$ ) correlation matrix (if unstructured correlation matrix failed) will be used within each prodrome event and the two prodrome events will be assumed to be independent. The treatment effect will be expressed in terms of the geometric mean of the odds ratios of ubrogapant 100 mg

[figure not shown]

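### The additional FDS responder in SAP 10.1 needs normal function only at recorded timepoints, so a partly missing event with no recorded disability counts as a success through 24 hours

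*SAP*

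**What the plan says.** Protocol 8.10 schedules the FDS as follows: "The measure will be assessed at predose (baseline) and 1, 2, 3, 4, 6, 8, 24, and 48 hours". Seven of the postdose ratings fall within 24 hours.

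SAP 10.1 builds an additional endpoint from those seven. An event is a "responder if a participant records no disability, able to function normally at all the observed timepoints FDS", and a non-responder otherwise. The model is stated: "The data will be analyzed using the same primary GLMM model with an additional covariate of predose baseline FDS score". The section does not say how many entries are needed, whether the 24-hour entry must be present, or how an event with no FDS entry is scored. The general rule in SAP 8.1 is a "GLMM in the observed binary response variable unless an imputation method is specified", and none is specified here.

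The primary endpoint is handled differently. Protocol 9.4.1.2 says: "If a participant did not report moderate/severe headache and has a missing 24-hour recall assessment, that participant will be counted as indeterminable". The version history in SAP 13.0 likewise treats a missing 48-hour headache entry as making the 48-hour endpoint indeterminable.

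The second secondary endpoint also uses the FDS but is a separate analysis. SAP 8.4.1 says: "The repeated binary responses will be analyzed using a GEE model with a logit link".

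**The concern.** An event that is normal at 1 hour and then has no further entries is scored as normal function through 24 hours, although a qualifying prodrome event is one in which headache is expected 1 to 6 hours later. An event with all seven entries and a single mild rating is scored as a failure. The fewer the entries, the easier the success.

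The 24-hour entry is the most exposed. A qualifying event requires diary availability only for the next 8 hours (Protocol 4.1 and 6.3.1), and the request to stay awake also covers 8 hours (Protocol 5.3.3).

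No planned analysis would show the effect. The non-responder and multiple-imputation analyses in SAP 8.2 act on indeterminable endpoints, and under this rule an event with at least one FDS entry is never indeterminable.

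What is at stake is how a descriptive percentage is read. Secondary hypothesis 2 is worded as a "proportion of participants who are able to function normally over 24 hours after taking the double-blind study intervention during the prodrome", whereas its GEE yields a geometric mean of odds ratios. The SAP 10.1 percentage is the FDS figure most easily quoted for that wording.

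**Working it through.** The plan gives no figure for this endpoint, so there is none to reproduce. The seven timepoints and the scoring rule come from SAP 10.1. The per-timepoint rate of normal function p, the latent within-event correlation ρ and all missingness rates are assumptions.

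**1. Direction, without assumptions.** For an event with at least one entry left, deleting an entry either leaves the score unchanged or removes the only recorded disability and turns a failure into a success. It never does the reverse.

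**2. How much easier success becomes.** With independent timepoints and a fraction m of entries missing at random, P(responder) = [1 − (1 − m)(1 − p)]^7. At p = 0.90:
- m = 0: 0.90^7 = 0.478
- m = 0.10: 0.91^7 = 0.517
- m = 0.20: 0.92^7 = 0.558

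With correlated entries (Gaussian copula, simulated, ρ 0.4 to 0.8), the chance of scoring as a responder is:

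| Entries recorded | p = 0.50 to 0.60 | p = 0.85 |
|---|---|---|
| all seven | 9% to 35% | 50% to 68% |
| first two only | 32% to 50% | 75% to 79% |
| first one only | 50% to 60% | 85% |

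**3. No true effect, early stopping that differs by arm.** Take p = 0.55 in both arms. Let a fraction t of events stop after two entries: 5% on ubrogepant, 15% on placebo. With P7 and P2 the chances that all seven, or the first two, are normal, the current rule gives (1 − t)P7 + t·P2. At ρ = 0.4, P7 = 0.1223 and P2 = 0.3673:
- ubrogepant: 0.95 × 0.1223 + 0.05 × 0.3673 = 0.1345
- placebo: 0.85 × 0.1223 + 0.15 × 0.3673 = 0.1590
- odds ratio: (0.1345/0.8655) / (0.1590/0.8410) = 0.82

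At ρ = 0.6 and 0.8 the odds ratios are 0.89 and 0.94. Swapping the stopping rates between arms reverses the direction.

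**4. Scattered missing entries (p = 0.85, ρ 0.3 to 0.7).**
- No true effect, 5% against 10% of entries missing: odds ratio 1.02 to 1.06 in favour of the arm with more missing. With 5% against 20%: 1.11 to 1.20.
- True odds ratio 1.64 (ρ = 0.5; p = 0.82 on placebo, 0.88 on ubrogepant), equal random missingness: 1.64 at 10% and 1.63 at 20%.
- Same true effect, impaired entries missed more often (30% against 5%) by the same mechanism in both arms: responder rates rise from 0.48 to 0.56 and from 0.61 to 0.67, and the odds ratio is 1.63.

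**5. Alternative rules in the scenario of step 3.**

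| Rule | Odds ratio at ρ = 0.4 / 0.6 / 0.8 |
|---|---|
| current, observed timepoints only | 0.82 / 0.89 / 0.94 |
| incomplete all-normal event = non-responder | about 1.13 to 1.17 |
| incomplete all-normal event excluded | about 1.09 |
| multiple imputation within treatment | about 1.00 |

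At ρ = 0.4, non-responder imputation gives 0.95 × 0.1223 = 0.1162 against 0.85 × 0.1223 = 0.1040, an odds ratio of 1.13. Imputation restores P7 in both arms because stopping here is unrelated to the unrecorded entries.

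**The case against.** The strongest reply concerns weight. The endpoint is an unranked addition: it is not among the HEOR endpoints of SAP 3.5 or in SAP Table 1, and it is outside the testing sequence of SAP 12.0. That stands. A reader might infer that the rule undermines the second secondary endpoint. The documents do not support this, because the GEE and the by-timepoint FDS models use each recorded rating and never apply the rule.

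A reader might also take this as the only per-participant responder analysis of functioning over 24 hours. It is not. SAP 10.1 also plans an Activity Limitation responder analysis from one 24-hour recall item, which cannot be partly missing. The FDS endpoint is only the FDS-based one.

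The size is assumption. Nothing in the documents suggests that 15% of placebo events would stop after two entries. The 8-hour diary condition, the advice on dosing time (Protocol 6.3.1) and possible reminders (Protocol 8) work against early stopping. Equal missingness barely moves the odds ratio. All of this stands, and it limits the claim to inflated percentages and a possible, unquantified bias in the comparison.

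The contrast with the primary endpoint is imperfect: there the deciding item is a 24-hour recall, not every intermediate entry. That is fair. But the documents describe no FDS recall item that could cover missed ratings, so incomplete FDS events are less well covered, not better.

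Finally, observed could be read as scheduled, so that a missing entry makes a failure. This is the less natural reading, but the wording does not exclude it, and the choice matters. With no true effect, p = 0.85, ρ = 0.5 and 5% against 10% of entries missing, the odds ratio is 1.05 on one reading and 0.57 on the other.

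**Conclusion.** The concern holds for this one endpoint. As written, SAP 10.1 scores an incomplete event with no recorded disability as a success through 24 hours. The upward push on the responder percentages follows from the rule itself wherever a missing entry would have been the only disability recorded. Bias in the odds ratio needs missingness that differs by treatment. Under the assumptions shown it ranged from 0.82 to 1.20 with no true effect, and the actual size cannot be known from the documents.

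A reader might infer that the rule favours ubrogepant. The documents do not support a direction: if worsening attacks stopped more placebo diaries early, the comparison would move against the drug. No result under type I error control is affected. The definition should be corrected, but as an additional endpoint it does not call the trial's main conclusions into question.

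**What to change.** In SAP 10.1, define three outcomes for each event:
- non-responder if any recorded FDS from 1 to 24 hours is above 0;
- responder if all seven entries are recorded as 0;
- indeterminable if one or more entries are missing and none recorded is above 0 (this also covers an event with no entries).

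Analyse indeterminable events mainly by multiple imputation of the missing FDS entries within treatment. The sequential method of SAP 8.2 can be adapted, but its screening covariate is based on headache, so earlier FDS entries and the predose FDS score should be the predictors instead. Report non-responder imputation and the present observed-timepoints rule only as sensitivity analyses, because neither non-responder imputation nor simple exclusion is neutral when missingness differs by arm. Tabulate the number of FDS entries per event by treatment so that the reader can judge the risk.

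The cost is a derivation change and a short FDS-specific imputation specification. The reported responder percentages will be lower than under the present rule.
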